7. APPENDICES

7.1. General analytic definitions

Definitions below correspond to calculation rules for expressions defined in [Section 4](#) as well as definition of value prior to treatment / under treatment, first and last IMP intake dates and other general definitions.

7.1.1. Value prior to treatment / under treatment

Table (7.1.1) 1 - Definition of value prior to treatment

General definition	
For assessments without time collected Corresponding assessment date \leq date of the first IMP intake + X1 _{sup} days	X1 _{sup} = 0
For assessments with time collected Corresponding assessment date/time \leq infusion start date/time of the first IMP intake + X1 _{sup} days	
Specific definition	
For ESSDAI, ClinESSDAI and PhGA Corresponding assessment date = date of visit at W000 \leq date of the first IMP intake + X1 _{sup} days	
For ESSPRI, MFI, PGA, SF-36 Corresponding assessment date = date of visit at W000 \leq date of the first IMP intake + X1 _{sup} days	

Table (7.1.1) 2 - Definition of value under treatment

General definition	
For assessments without time collected	
On W000-W013 Period if W013 visit done Date of first IMP intake + X1 _{sup} ^(*) days \leq Corresponding assessment date \leq Date of W013 visit + X2 _{sup} days	X2 _{sup} = 0
On W000-W013 Period if W013 visit not done Date of first IMP intake + X1 _{sup} ^(*) days \leq Corresponding assessment date \leq Date of last IMP intake on the W000-W013 period + X2 _{sup} days	X2 _{sup} = 21
On W000-W028 Period Date of first IMP intake + X1 _{sup} ^(*) days \leq Corresponding assessment date \leq Date of last IMP intake on the W000-W028 period + X2 _{sup} days	X2 _{sup} = 85
For assessments with time collected	
On W000-W013 Period if W013 visit done Infusion start date/time of the first IMP intake + X1 _{sup} ^(*) days \leq Corresponding assessment date/time \leq Date of W013 visit + X2 _{sup} days	X2 _{sup} = 0
On W000-W013 Period if W013 visit not done Infusion start date/time of the first IMP intake + X1 _{sup} ^(*) days \leq Corresponding assessment date/time \leq Date of last IMP intake on the W000-W013 period + X2 _{sup} days	X2 _{sup} = 21
On W000-W028 Period Infusion start date/time of the first IMP intake + X1 _{sup} ^(*) days \leq Corresponding assessment date/time \leq Date of last IMP intake on the W000-W028 period + X2 _{sup} days	X2 _{sup} = 85

^(*) cf. definition of value prior to treatment.

7.1.2. First and last IMP intake dates

Because all IMP intake dates are complete, no substitution will be defined.

7.1.3. Other dates

If no specific management of dates is defined, missing information is substituted as defined below:

Table (7.1.3) 1 - Substitution rules of dates if no specific management is defined

Date to substitute		Substituted date
Date	../mmm/yyyy	01/mmm/yyyy
	../.../yyyy	01/JAN/yyyy
	../.../....	No substitution

Note:

../mmm/yyyy = missing day
 ../.../yyyy = missing day and month
 ../.../.... = missing date

For assessments with time also collected and useful for the analysis, substitution rules are as follows:

Table (7.1.3) 2 - Substitution rules of dates and times if no specific management is defined

Date and time to substitute		Substituted date and time
Date	dd/mmm/yyyy hh-...	dd/mmm/yyyy hh:00
	dd/mmm/yyyy ...-...	dd/mmm/yyyy 00:00
	../mmm/yyyy ...-...	01/mmm/yyyy 00:00
	../.../yyyy ...-...	01/JAN/yyyy 00:00
	../.../.... ...-...	No substitution

Note:

hh-... = missing minutes
 ...-... = missing time
 ../mmm/yyyy = missing day
 ../.../yyyy = missing day and month
 ../.../.... = missing date

7.2. Specific analytic definitions and data handling conventions

7.2.1. Study participants

7.2.1.1. Demographic data and other baseline characteristics

7.2.1.1.1. Demographic data

Age (years) is calculated in the ClinTrial database as:
Year of selection visit (ASSE) – Year of birth

7.2.1.1.2. History of the Sjögren's disease

The duration of the disease (years) is defined as:
(Date of selection visit (ASSE) – Date of diagnosis) / 12.
The result is rounded to the nearest integer.

7.2.1.1.3. Relevant medical and surgical history other than the PSS symptoms

The existence of a history (Yes/No) is defined from the presence, or not, of a Primary system organ class and/or Preferred term.

7.2.1.1.4. Previous treatments

Previous treatments are all treatments received and stopped within 12 months before screening visit (including vaccinations). All vaccinations deemed necessary by the investigator for the patient should be up to date before inclusion. Therefore, the corresponding last vaccinations and last boosters will be considered and reported as previous treatment (even if administered more than 12 months prior to the screening visit).

The anatomical therapeutic chemical classification (ATC code = 5 digits) is composed of 4 levels:

- The first (1 digit) represents the anatomo-physiological class.
- The second (2 digits) represents the pharmacological class.
- The third (1 digit) represents the pharmacological sub-class.
- The last (1 digit) represents the therapeutic class.

Previous treatment is defined as any treatment with associated stop date strictly inferior to the first IMP intake date.

Note: In case of patient included and/or randomised but not treated, previous treatment is defined as any treatment with associated stop date strictly inferior to date of inclusion visit.

Only treatment with an Anatomical therapeutic chemical classification and/or a Preferred name is considered.

CL2-95011-001 - Statistical Analysis Plan | VV-TMF-116033 | 2.0

The **rules for substitution** of missing or incomplete previous treatments stop dates are as follows:

Table (7.2.1.1.4) 1 - Substitution rules of previous treatments stop date

Date to substitute		Substituted date
Stop date	../mmm/yyyy	If patient died same month and year then Date of death Else Last day of the month/mmm/yyyy
	../.../yyyy	If patient died same year then Date of death Else 31/DEC/yyyy
	../.../....	If patient died then Date of death Else No substitution (i.e., treatment considered as still ongoing)

Note: ../mm/yyyy = missing day
../.../yyyy = missing day and month
../.../.... = missing date

The lists of the considered ATC codes for specific previous treatments to Sjögren disease are the excel files:

- 2602.0 Systemic and local treatments containing corticosteroids DDB320221.
- 4306.0 Treatments containing antimalarial DDB320221.
- 4302.0 Treatments containing methotrexate DDB320221.
- 3700.2 Non-steroids antiinflammatory drugs (NSAIDS) DDB320221.
- 4309.0 Treatments containing cevimeline and pilocarpine DDB320221.
- 4324.0 Ocular topics for S95011 DDB320221.
- 4382.1 Drugs known to induce dry mouth and dry eyes DDB320221.
- 1728.2 Treatments containing an alkylating agents DDB320211.
- 3432.1 Treatments containing rituximab or other B cell depleting agents DDB320221.
- 4299.0 Treatments containing Abatacept DDB320221.
- 4300.0 Treatments containing Belimumab DDB320221.
- 4303.0 Treatments containing Tumor Necrosis Factor (TNF) inhibitor DDB320221
- 4305.0 Treatments containing tocilizumab DDB320221
- 4308.0 Treatments containing specific immunosuppressants for 95011 DDB320221.
- 4618.0 Treatments containing Janus Kinase associated inhibitors DDB320221.

Other ATC codes in the ClinTrial database are for non-specific previous treatments.

7.2.1.2. Extent of exposure and treatment compliance

Number of infusions per patient is defined as:

Number of visits (among W000, W002, W004, W007, W010) with non-missing IMP intake date and the question “Did the patient receive the IMP infusion?” = Yes

Time between two IMP administrations (i and i+1) is derived as (days):

By visit i+1: Infusion stop date of the IMP intake at the visit i+1 – infusion stop date of the IMP intake at the visit i.

7.2.1.3. Concomitant treatments

The **anatomical therapeutic chemical classification** (ATC code = 5 digits) is composed of 4 levels:

- The first (1 digit) represents the anatomo-physiological class.
- The second (2 digits) represents the pharmacological class.
- The third (1 digit) represents the pharmacological sub-class.
- The last (1 digit) represents the therapeutic class.

The **existence of a concomitant treatment** (Yes/No) is defined from the presence, or not, of an Anatomical therapeutic chemical classification and/or Preferred name.

The **periods considered for the analysis** are:

- At inclusion for which treatments with start date \leq inclusion date and stop date \geq inclusion date or missing are taken into account.
- During the W000-W013 treatment period for which treatments:
 - With start date \geq first IMP intake date and $<$ last IMP intake date, or
 - With start date \leq first IMP intake date and stop date \geq first IMP intake date or missing are taken into account.
- After the last IMP intake for which treatments with start date $>$ last IMP intake date are taken into account

Concomitant treatments could be considered in one or several of the possible analysis periods.

The lists of the considered ATC codes for specific concomitant treatments to Sjögren disease are the excel files:

- 2602.0 Systemic and local treatments containing corticosteroids DDB320221.
- 4306.0 Treatments containing antimalarial DDB320221.
- 4302.0 Treatments containing methotrexate DDB320221.
- 3700.2 Non-steroids antiinflammatory drugs (NSAIDS) DDB320221.
- 4309.0 Treatments containing cevimeline and pilocarpine DDB320221.
- 4324.0 Ocular topics for S95011 DDB320221.
- 4382.1 Drugs known to induce dry mouth and dry eyes DDB320221.

Other ATC codes in the ClinTrial database are for non-specific concomitant treatments.

The following **rules for substitution** of missing or incomplete start and stop dates are so that the concomitance period is maximised:

Table (7.2.1.3) 1 - Substitution rules of concomitant treatments intake dates

Date to substitute	Substituted date	
Start date	../mmm/yyyy	01/mmm/yyyy
	../.../yyyy	01/JAN/yyyy
	../.../....	If stop date is non-missing and inferior to selection date then: Stop date Else: Selection date
Stop date	../mmm/yyyy	If patient died same month and year then Date of death Else Last day of the month/mmm/yyyy
	../.../yyyy	If patient died same year then Date of death Else 31/DEC/yyyy
	../.../....	If patient died then Date of death Else No substitution (i.e., treatment considered as still ongoing)

Note: ../mm/yyyy = missing day
../.../yyyy = missing day and month
../.../.... = missing date

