6.2. IMPs dispensing

The treatment group will be allocated *via* IWRS using a central randomisation (2:1) to S95011 or placebo with stratification by baseline intake of oral corticosteroids (yes/no) and baseline intake of antimalarial (*e.g.* chloroquine, hydroxychloroquine, quinacrine) (yes/no).

At inclusion visit (W000), patient will be randomised to S95011 or placebo by IWRS. A connection to the IWRS should be performed at each concerned visit (from W000 to W010) to know the allocated kit numbers to be used for the infusion bag preparation (see details in IWRS manual).

Therapeutic units will be identified by a 6-digit number for identification, tracking and stock management purposes. For each administration, 9 vials of IMP will be delivered.

The detachable portion of the label on the IMP box must be stuck by the investigator's staff on the prescription form when the IMPs are dispensed by a pharmacist.

For each patient, the IMP will only be dispensed during the study. At W010 visit, the last administration of the IMP will be performed.

At last study visit, the investigator will propose a treatment adapted to the nature of the clinical state of the patient.

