1.1.2. Endpoints

The primary efficacy endpoint is the change from baseline in ESSDAI total score to W013.

The secondary efficacy endpoints are:

- ESSDAI score by domain and total score at each visit (value & change).
- ESSPRI score by symptom and total score at each visit (value & change).
- Proportion of patients with ≥ 3 points, ≥ 5 points, ≥ 7 points of improvement from baseline in ESSDAI at each visit.
- Proportion of patients with ≥ 1 point, ≥ 2 points, ≥ 3 points of improvement from baseline in ESSPRI at each visit.
- Proportion of patients with ≥ 3 points of improvement in ESSDAI and with ≥ 1 point of improvement in ESSPRI from baseline at each visit.
- Proportion of patients with a STAR total score ≥ 5 at each visit (value).
- Proportion of patients with a CRESS total score ≥ 3 at each visit (value).
- Fatigue (MFI) by domain, quality of life (SF-36) for mental and physical domains, physician and patient's global assessment of the disease activity (NRS) at each visit (value and change).
- Tear gland function: Schirmer's test and in OSS on the most affected eye and for the mean of both eyes at each visit (value and change).
- Salivary gland function: unstimulated and stimulated salivary flow rate at each visit (value and change).

The other secondary endpoints are:

- **Safety:** The safety and tolerability assessed by incidence of adverse events (AEs), change over time in safety parameters (vital signs, biological laboratory) and incidence of abnormal safety parameters throughout the study.
- **Pharmacokinetics:** Pharmacokinetics of S95011 in serum samples:
 - Pre-dose (before the start of the IMP infusion) at W000, W002, W004, W007, and W010.
 - Right after the end of the IMP infusion and in the [1-3h] interval after the end of the IMP infusion at W000 and W010.
 - Between W011 and W012, and at W013, W016, W019 and W028.

CL2-95011-001 - Statistical Analysis Plan | VV-TMF-116033 | 2.0

- **Pharmacodynamics:** Receptor Occupancy (RO) of S95011 in blood samples:
 - Pre-dose (before the start of the infusion) at W000, W002, W004, W007 and W010.
 - Right after the end of the infusion of the IMP at W000 and W010.
 - At W013, W019, W028.
- **Incidence of ADA** in serum samples:
 - Pre-dose (before the start of the infusion) at W000, W002, W004, W007 and W010.
 - At W013, W019, W028.

The exploratory endpoints are:

- **In blood:**
 - Lymphocytes subsets (PBMC) assessed at W000, W004, W007, W013.

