1.1.4. Study plan

The study is divided into the following periods:

- **Screening period without study treatment:** from selection visit (ASSE within 28 days prior to W000) to inclusion visit (W000), after signing the ICF, in order to check eligibility of patients.
- **Randomised and double-blind treatment** period: from W000 to W013 (study drug administration at W000, W002, W004, W007, W010) with two-parallel groups (750 mg of S95011 and matching placebo), with stratification by baseline intake of oral corticosteroids (yes/no) and baseline intake of antimalarial (*e.g.* chloroquine, hydroxychloroquine, quinacrine) (yes/no).
- **Safety follow up period without study treatment:** 15 weeks with one visit at W019 and one at W028. This follow-up period will allow sufficient time for monitoring safety until 5 half-lives of S95011. In addition, it is anticipated that more than 97% of patients have RO < 95% at W028 (meaning that almost no pharmacological effect of the product is expected).

[figure not shown]
The expected duration of patient participation will be 32 weeks maximum.

Study treatments are supplied as follows:

- **During the screening period (from ASSE to W000)**, no treatment will be dispensed.
- **From the day after inclusion until the day of W013 visit**, patients take one (1) IV infusion of 750 mg of S95011 or matching placebo every two weeks (q2w) for the first month (W000, W002, W004) and then every 3 weeks (q3w) until W010 (W007, W010). S95011/matching placebo will be provided to the site in 2 mL extractable volume vials containing 100 mg of S95011/matching placebo (50 mg/mL) concentrate for solution for intravenous administration. As treatment is dispensed during a double-blind period, the appearance and form of S95011 vials and placebo vials as well as the solutions to be administered will be similar: a colourless to slightly yellow, clear to slightly opalescent aqueous solution.
- **From the day after W013 visit until the day of W028 visit**, follow-up period.

The study plan is shown in [Figure \(1.1.4\) 1](#).

Figure (1.1.4) 1 - Study plan

*One blood sample will be performed for PK assessment between W011 and W012 and at W16 (± 5 days), at site or not according to local facilities.

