7.2.2. Efficacy

7.2.2.1. Intercurrent Event (IE)

IE1: Study drug discontinuation for major worsening of primary Sjögren's syndrome.

IE2: Increase or initiation of authorized medication for pSS.

IE3: Study drug discontinuation for AE related to study drug.

IE4: Study drug discontinuation for other reasons (non-medical reason, AE not related...).

IE5: Switch of treatment group (error of dispensation).

IE6: Decrease or stop of authorized medication for pSS.

For all efficacy endpoints, a flag for each intercurrent event (IE) will be created to identify the values collected post-IE vs the values before or on the IE date. As a reminder, the IE date is the date of the start of IE.

One global IE flag will be derived to determine which IE occurs first. In case a patient is concerned by several IEs, the first event will be considered. If several IE occurred the same day, IE will be considered to be more conservative in the following order: IE1; IE2; IE3; IE4; IE5, IE6.

Study drug discontinuation for major worsening of primary Sjögren's syndrome (IE1) is defined as follow:

- AE related to pSS leading to study drug discontinuation.

Increase or initiation of authorized medication (IE2) is defined as follows:

- Any increase or initiation of a new dose of corticosteroids (oral prednisone or equivalent) within 4 weeks prior to W013 visit.
- Any intramuscular, IV, or intra-articular corticosteroids within 4 weeks prior to W013 visit.
- Any increase or initiation of new dose of topical corticosteroids within 2 weeks prior to W013 visit.

CL2-95011-001 - Statistical Analysis Plan | VV-TMF-116033 | 2.0

- Any increase or initiation of new dose of antimalarials (e.g. chloroquine, hydroxychloroquine, quinacrine) after randomisation (W000).
- Any increase or initiation of new dose of methotrexate after randomisation (W000).
- Any change in route of administration of methotrexate within 4 weeks prior to W013 visit.
- Any increase or initiation of new dose of regularly scheduled Non-steroidal anti-inflammatory drugs (NSAIDs) within 2 weeks prior to W013 visit.
- Any increase or initiation of new doses of cevimeline or oral pilocarpine within 2 weeks prior to W013 visit.
- Any increase or initiation of new doses of Ocular topics (excluding artificial tears, gels, lubricants, antibiotherapy) within 90 days prior to W013 visit.

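### The concomitant-treatment period labelled W000-W013 closes to new drugs before the W010 infusion, so 22 of its 92 possible start days are missing from that table, and one of them belongs to no period

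*SAP*

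**What the plan says.** SAP 4.2.2 promises a description of concomitant treatments at inclusion, during W000-W013 and after the last IMP intake. SAP 7.2.1.3 gives the date rules.

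- **At inclusion:** the drug starts on or before the inclusion date and is still ongoing then.
- **The W000-W013 period** ("During the W000-W013 treatment period for which treatments"): a drug enters by one of two routes. It is newly started, with a start date on or after the "first IMP intake date and $<$ last IMP intake date, or" it started on or before the first intake and was still ongoing at that date.
- **The later period:** "After the last IMP intake for which treatments with start date" strictly later than the last intake are counted, with no upper limit.

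The same section adds: "Concomitant treatments could be considered in one or several of the possible analysis periods".

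On timing, Protocol 6.2 states: "At W010 visit, the last administration of the IMP will be performed". SAP 1.1.4 describes the treatment period as running "from W000 to W013 (study drug administration at W000, W002, W004, W007, W010"). SAP 1.1.2 sets the time of the main outcome: "The primary efficacy endpoint is the change from baseline in ESSDAI total score to W013".

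Elsewhere the SAP ends this period at W013. Treatment-emergent adverse events (SAP 4.4.1) and values under treatment (Table (7.1.1) 2) run to the W013 visit date included, or to last IMP intake plus 21 days if the visit was not done.

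**The concern.** The label promises a summary up to W013, but for new drugs the rule stops just short of W010. A reader of the W000-W013 table would take it to cover the whole run-up to the primary assessment. In fact it would show no drug started in the last three weeks before that assessment.

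The strict inequalities on both sides also leave the last infusion date unassigned. Infusion days are plausible start dates: Protocol 6.1 foresees symptomatic drugs, including NSAIDs and corticosteroids, for acute infusion reactions.

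What is at stake is whether a set of descriptive tables is accurate and consistent with the rest of the SAP.

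**Working it through.** The plan states no figure for this point, so there is none to reproduce. The check applies the three date rules as written to every possible start day of a drug that is ongoing once started.

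**Inputs**
- First infusion: W000, day 0 (SAP 1.1.4).
- Last infusion for a completer: W010, day 10 × 7 = 70 (Protocol 6.2).
- End of the treatment period: W013, day 13 × 7 = 91 (SAP 1.1.4).
- End of follow-up: W028, day 28 × 7 = 196 (SAP 1.1.4).
- Visit windows: ±2 days at W010 and W013, relative to W000 (Protocol Table (4.1.2) 1).

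**Nominal schedule, start days 0 to 91 (92 days)**

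| Start day | W000-W013 period | Later period | Number of days |
|---|---|---|---|
| 0 to 69 | yes | no | 70 |
| 70 (last infusion) | no, 70 is not below 70 | no, 70 is not above 70 | 1 |
| 71 to 91 | no | yes | 21 |

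Missing from the W000-W013 table: 1 + 21 = 22 days, and 22/92 = 24%. Of these, 21 are moved to the later period and 1 is in neither.

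**With the visit windows**
- W010 two days late and W013 two days early (days 72 and 89): the gap is 17 days, and 1 + 17 = 18 of 90 start days are missing (20%).
- W010 two days early and W013 two days late (days 68 and 93): the gap is 25 days, and 1 + 25 = 26 of 94 are missing (28%).
- The last infusion date is unassigned in both cases.

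**Mixing in the later period.** With all data to W028, that period spans days 71 to 196, which is 196 − 70 = 126 days. The part before the end of W013 is 21 days (21/126 = 17%). The rest is 126 − 21 = 105 days, the 15-week follow-up.

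**Edge cases**
- If a patient has only one infusion, a drug started that day and not stopped before it enters through the second route, because it starts on the first intake date. The one-day gap therefore needs at least two infusions.
- For a patient who stops early, the window closes at that patient's own last infusion, so more of the period is lost.

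**After the change.** With an upper bound of day 91 included, all 92 start days fall in the W000-W013 period.

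**The case against.** The strongest reply is that splitting at the last infusion is a sensible exposure-based choice, that SAP 4.2.2 names the later period openly, and that nothing of consequence depends on these tables. Much of this stands, and it rules out several stronger readings.

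- **That drugs started between W010 and W013 are lost.** A reader might infer this, but they are tabulated in the later period. Only starts on the last infusion date fall outside both the during and the after period.
- **That they are always buried in follow-up data.** The main analysis covers ASSE-W013 and later data are described afterwards (SAP 1). The SAP does not state the data cut for this table. If it is run on ASSE-W013 data, the later period would hold, for completers, only starts between W010 and W013. Mixing with the 15-week follow-up is certain only in the final analysis.
- **That the primary result is affected.** It is not. SAP 7.2.2.1 gives each intercurrent event its own flag and date. The windows for medication changes are separate from these periods, for example "Any increase or initiation of new dose of topical corticosteroids within 2 weeks prior to W013 visit". No estimate, test or imputation uses the periods of SAP 7.2.1.3.
- **That the table should reconcile with the intercurrent-event counts.** No section requires this, and it would not do so even with the right bound. IE2 and IE6 count dose increases, decreases, stops and route changes in drug-specific windows, whereas the table counts patients taking a drug, including unchanged background therapy.

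The reply does not explain the label or the gap. If the split is by exposure, the period should not be called W000-W013 when the SAP elsewhere ends that period at the W013 visit. The sentence allowing a drug to count in several periods does not rescue the last infusion date, since a drug must still meet a period's date rule. The SAP gives no reason for the difference. The same section says that its substitution rules for incomplete dates are chosen to make the concomitant period as long as possible, and a bound that shortens it runs against that aim.

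**Conclusion.** The rule is wrong as written, with a small effect. Followed literally, it produces a W000-W013 concomitant-treatment table that lacks 22 of 92 start days (24%; 20% to 28% across the visit windows). Of these, 21 are shown only in the later period, and the last infusion date is in neither for patients with at least two infusions.

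The figures assume a completer whose last infusion is at W010 and a drug newly started after the first infusion. Drugs already ongoing at the first infusion are counted correctly. The percentages are shares of calendar days, not of treatments; the documents do not say how many drugs were started in that window.

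The consequence is limited to descriptive tables. The documents do not support a claim of bias in the ESSDAI comparison or of misclassified intercurrent events.

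**What to change.** In SAP 7.2.1.3, change the upper bound for newly started drugs in the W000-W013 period to a start date on or before the W013 visit date, or on or before last IMP intake plus 21 days if that visit was not done. This is the bound already used in SAP 4.4.1 and Table (7.1.1) 2. It closes both gaps and needs no new data: one bound in the text and one in the program.

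The later period can stay as it is, because the SAP lets a drug count in several periods. Drugs started on days 71 to 91 would then appear in both tables, and a footnote should say so.

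If the sponsor prefers periods that do not overlap, the later one should begin after the new bound. It would then need a new label in SAP 4.2.2 and in the table templates, which costs slightly more.
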